We will retrieve data on our main outcomes from the IMOX study in our analysis. Only electronic data will be used and no biologic material will be transferred from the IMOX project to ANIMOX. The population will be stratified according to anesthetic technique, which, according to the standard operating procedure, is either total intravenous anesthesia with propofol and remifentanil or volatile anesthesia with sevoflurane combined with a fast acting opioid (remifentanil or sufentanil). Patients anaesthetized with other techniques including epidural or other regional blocks will be excluded from the analysis.

Biological samples

To characterize the immunological response to surgery we obtain blood samples for analysis on postoperative day -1, 1, 2, 3 and 10 (or at the visit on day 10-14 where pathology results are given).

Handling of blood samples

Blood samples will be drawn by a trained professional and analyzed immediately at the standard lab facilities at Hvidovre Hospital and destroyed immediately hereafter. The results will be accessible in Sundhedsplatformen.

Primary outcome:

The primary outcome will be changes in neutrophil to lymphocyte ratio from day 0 to day 1. Neutrophil to lymphocyte ratio has been linked to poor outcome after colorectal cancer surgery. The ratio will be estimated using absolute numbers from differential counts pre and postoperatively.

Blood samples

Standard blood samples will be obtained and analyzed immediately at each time point. These include Hgb, Leucocytes including a differential count, thrombocytes, ALAT, LDH, Alkaline phosphatase, bilirubin, INR, albumin, Na, K, Creatinine, CRP and Glucose.

Quality of Recovery – 15 questionnaire

At each time point (day -1, 1,2 and 10) the patients are asked to fill in the validated Quality of Recovery Questionnaire QoR-15²⁷. The QoR-15 questionnaire results in a score of 0–150. These outcome measures will be correlated with changes in immunologic outcome measures in the perioperative period.

Guidelines for oral and written consent and participant timeline

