Patients scheduled for laparoscopic hemicolectomy at Hvidovre Hospital will be screened for eligibility. 300 laparoscopic colon resections for cancer are performed at this facility each year and most of these are scheduled for total intravenous anesthesia with epidural anesthesia. With an inclusion rate of 50% we expect to be able to

include 30 participants that completes the study and does not meet the withdrawal criteria within 26-52 weeks.

We expect to begin inclusion in January 2019 and to finish the trial by 31st December 2019.

Data collection and management

To screen for eligibility to be included in the study we will request and obtain data on tumor stage, age, known immune defects, ASA-score, type of surgery, planned anaesthesia type and use of steroids.

After informed consent and inclusion in the study, data on demographics (comorbidities, age, sex), disease stage (clinical and pathological tumor histology), perioperative management (anesthesia type, medication, surgical procedure) and adverse events up to 30 days postoperatively will be obtained from the patient file. Nurses at the Surgical Ward will be trained to encourage participants to fill in the QoR-15 questionnaires. The questionnaires will be kept with the patient in a folder that will be returned at the time of discharge. The patient will bring one QoR-15 questionnaire home to fill in at day 10. This questionnaire will be returned at the pathology result visit at day 10-14.

Blood samples will be taken and handled by a trained health care professional and brought to the laboratory for preparation and analysis within one hour.

Patients who are discharged before blood samples are taken on day 1,2, and 3 will be asked if they wish attend the blood sampling as out-patients at the same timepoints. Patients who does not show up to, or does not have the final blood samples taken at the time of out-patient pathology results will be contacted and encouraged to have the final blood samples taken and return the last QoR-15 questionnaire.

Study data will be stored according to guidelines from the Danish Data Protection Agency and “databeskyttelsesforordningen” and “databeskyttelsesloven” will be adhered to.

Statistical analysis plan

Data will be analyzed using R, SAS institute or SPSS. All tests will be two-sided with $p < 0.05$ considered to be significant.

Data analysis

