Data from the Hvidovre population and the Zealand University Hospital population will be combined to evaluate the effects of inhalational anesthesia (sevoflurane and opioid), total intravenous anesthesia (propofol and remifentanyl) and total intravenous anesthesia (propofol and remifentanyl) combined with epidural anesthesia (bupivacaine with opioid). Only electronic data will be used from the IMOX project – no biologic material will be transferred.

Baseline and clinical characteristics for patients, stratified for anesthesia type will be presented as frequencies for nominal, dichotomous and ordinal variables and medians with IQR for continuous variables. Outcome variables will be presented and described with appropriate tests. Depending on whether data is normally distributed or not, differences between the groups will be assessed using parametric or non-parametric statistics, respectively.

Risks, harms and inconveniences

Patients will receive the standard care at the respective hospital. The study does not influence any treatment or intervention related to the hospitalization.

Peripheral blood samples

Blood will be drawn from puncture of the cubic vein. The needle can cause minor discomfort including hematoma, which will disappear within few days.

QoR-15 questionnaires

Filling in the QoR-15 questionnaire will require a short amount of time and effort at the four time points.

Ethical considerations

Research within this field is until now very limited, but optimization of the anesthetic technique used for cancer surgery can benefit millions of people undergoing surgery for cancer in the future.

Approval from the regional scientific ethical committee is mandatory. Important modifications in the protocol will be communicated to the committee and approved before implementation.

Written consent from all participants will be obtained before inclusion as described above. Participants can at any time withdraw their consent.

All personal information about enrolled patients will be collected and protected according to Danish Law to ensure confidentiality before, during and after the study.

Data will only be assessed by participants of the study group according to the approval from the Danish Data Protection Agency.

Risk of random findings

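### The QoR-15 correlation has no term for anesthetic group or baseline, so if it is run on the combined cohorts, group differences alone can produce it

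*Combined protocol and SAP*

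**What the plan says.** The section on the QoR-15 questionnaire gives the timing: "At each time point (day -1, 1,2 and 10) the patients are asked to fill in the validated Quality of Recovery Questionnaire". The "questionnaire results in a score of 0–150", and no change score is defined. One sentence then sets out the analysis: "These outcome measures will be correlated with changes in immunologic outcome measures in the perioperative period". Neither that section nor the statistical analysis plan names the patients, the coefficient, the days to be paired, or any stratum or covariate.

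Under Data analysis, "Data from the Hvidovre population and the Zealand University Hospital population will be combined" in order to evaluate three anesthetic techniques, using unadjusted parametric or non-parametric tests. The correlation is not mentioned there.

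Blood is taken "on postoperative day -1, 1, 2, 3 and 10 (or at the visit on day 10-14 where pathology results are given". For the last form, Data collection and management says "The patient will bring one QoR-15 questionnaire home to fill in at day 10" and "This questionnaire will be returned at the pathology result visit at day 10-14".

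**The concern.** Every Hvidovre patient has intravenous anesthesia with an epidural, and IMOX patients with an epidural are excluded. Epidural use is therefore tied completely to hospital. The sample size supposes that NLR rises half as much in one group as in another. If the epidural group also reports better early recovery, for any reason including hospital routine, the pooled scatter holds two shifted clouds. A line drawn through both slopes downward even if each cloud is round. A reader could then take a difference between groups for a link between immune response and recovery in individual patients.

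Baseline raises a second, smaller issue. The immune side is a change and the QoR-15 side is, as described, a score. If preoperative QoR-15 and preoperative NLR are related, that relation can leak into the correlation unless both baselines are adjusted for.

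**Working it through.** **1. The plan's own figure.** A 50% smaller increase is 0.5 × 5.33 = 2.665. For two groups, two-sided 5% and 80% power, n = 2 × (1.960 + 0.842)² × 3.33² / 2.665² = 24.5, so 25 per group. This matches the stated 25, and 2.665 can serve as the plan's own between-group difference in NLR change. The plan gives no figure for the QoR-15 correlation.

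**2. Inputs for the pooled correlation.**
- From the Sample size section: NLR rise 5.33 v 2.665, SD 3.33, and 30 evaluable Hvidovre patients.
- From the Population section: 60 IMOX patients. This is an upper bound, because other techniques are excluded from the analysis; 30 is used as an assumed alternative.
- Assumed, not in the documents: QoR-15 SD 20; epidural advantage d of 8, 12, 16 or 20 points; zero correlation within each group; the two non-epidural techniques treated as one group.

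**3. Formula.** With p the share of epidural patients and k = p(1 - p):

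r = -k × 2.665 × d / √[(3.33² + k × 2.665²)(20² + k × d²)]

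Example with 30 v 60 and d = 20: k = 1/3 × 2/3 = 0.222. The numerator is 0.222 × 2.665 × 20 = 11.84. The denominator is √(12.67 × 488.9) = 78.7. So r = -0.15.

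The chance of p<0.05 uses Fisher's z. Here atanh(0.1505) × √87 = 1.41, which gives about 29%; simulation with 20,000 runs gives 30%.

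| QoR-15 advantage | r, 30 v 60 | p<0.05 | r, 30 v 30 | p<0.05 |
|---|---|---|---|---|
| 8 | -0.07 | 9% | -0.07 | 9% |
| 12 | -0.10 | 15% | -0.11 | 13% |
| 16 | -0.12 | 22% | -0.14 | 18% |
| 20 | -0.15 | 29-30% | -0.17 | 25% |

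In the same simulations, a partial correlation given group rejects in about 5% of studies in every row. For scale, the smallest significant r is about 0.21 with 90 patients and 0.25 with 60.

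**4. Baseline.** Assume 90 patients, a correlation of 0.5 between day -1 and day 1 QoR-15, a correlation rb between the two baselines of -0.3 to -0.5, a correlation s between baseline NLR and its change of -0.3 to -0.5, and no other link.
- Raw QoR-15 score against NLR change: r = 0.5 × rb × s, from 0.5 × 0.09 = 0.045 to 0.5 × 0.25 = 0.125. False positives about 7% to 23%.
- Change in QoR-15 against change in NLR: r = (0.5 - 1) × rb × s, from -0.045 to -0.125. False positives about 7% to 22%.
- Adjusted for both baselines: r about 0, false positives 5% to 6%.

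Under these assumptions a change score gives a bias of the same size with the opposite sign.

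**5. Timing.** Forms and blood share nominal days -1, 1 and 2; day 3 has blood but no form. At the last time point the form is due on day 10 and the blood on day 10 to 14, a gap of 0 to 4 days.

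**The case against.** The strongest reply is that pooling is inferred. The cohorts are combined to study anesthetic effects, and the plan says only that IMOX has similar primary and secondary outcomes, without naming QoR-15. If the correlation uses Hvidovre patients alone, all have the same technique and hospital, and the group problem disappears. That stands, and the point is conditional for this reason. Pooling remains the likelier reading, because the introduction promises to describe quality of recovery across the methods and Hvidovre supplies only one of them.

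Three stronger readings are tempting, and the documents do not support them:
- A reader might infer that the plan has chosen scores over changes. It defines only a score but does not exclude a change.
- A reader might infer that the gap of up to four days adds to the confounding. It cannot create a group difference. It can only weaken a real link, and only at the last time point, which may not be meant by the perioperative period at all.
- A reader might conclude that correlating change with change is the cure. Step 4 shows that it need not be.

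It is also fair to say that the spurious r is small, that the QoR-15 inputs are assumed, and that the study calls itself exploratory.

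**Conclusion.** The concern holds in conditional form. The correlation is specified without a group or baseline term. Run on pooled data, it can reach significance in roughly 9% to 30% of studies instead of 5% when nothing links recovery and NLR within groups. That range rests on the plan's NLR difference, the assumed SD of 20 and the assumed advantage of 8 to 20 points; a smaller QoR-15 difference would bring it closer to 5%. The baseline part rests wholly on assumed correlations. The primary outcome and the sample size are not affected. Severity is minor.

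**What to change.** State in the statistical analysis plan:
1. Which patients enter the correlation, and whether IMOX holds QoR-15. If it does not, or if only Hvidovre patients are used, say so and drop the group term.
2. The analysis at days 1 and 2, where form and blood share a nominal day: a partial correlation of QoR-15 with NLR change, given anesthetic group (three levels) and adjusted for day -1 QoR-15 and preoperative NLR. This replaces both a raw pooled correlation and a change-score correlation. Name the coefficient.
3. The last time point as descriptive only, with the actual dates of the last form and last blood draw recorded. The form need not be moved.

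The cost is a few lines of text and a date entry. The model spends four degrees of freedom (two for group, two for baselines), leaving 90 - 2 - 4 = 84 with 90 patients or 60 - 2 - 4 = 54 with 60. Patients without a day -1 form drop out of the adjusted analysis, so their number should be reported. Adjustment for group cannot separate the epidural from the hospital; it only keeps that joint difference out of the correlation.

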Colorectal cancer is a frequent type of cancer accounting for 600,000 deaths annually. Surgical resection remains the best treatment for long-term survival. However, studies suggest that events in the perioperative period can induce metastasis formation and tumor growth^{1,2,3}. Tumor cells are released into the blood stream during surgery and the surgical stress may create a favorable environment for dissemination of tumor cells into distant tissue^{4,5,6,7,8}. This is done by a cascade of pro-cancerous catecholamines, prostaglandins and cytokines combined with an impaired anti-cancerous cell mediated immune response^{9,10,11}.

Until recently, focus on the anesthetic management of cancer patients has been limited. Relatively small alterations in the perioperative anesthetic management may play a tremendous role in tumor progression⁹. Optimizing anesthesia to reduce the surgical stress response could improve recurrence rates and long-term outcomes for cancer patients by inhibiting perioperative metastasis formation. Regional anesthesia and amide local anesthetics are suspected to calm the immunologic storm of prostaglandins, catecholamines and cytokines when used in the perioperative phase^{12,13,14,15,16,17}. Furthermore, volatile inhalational anesthesia is thought to modulate the immune system in a pro-cancerous way, while propofol may have opposite effects^{18,19,20,21,22}. Many of these recent studies are statistically underpowered and susceptible to bias, and experts in cancer treatment and anesthesia have emphasized the need for further research within this specific field^{5,23,24}.

In this study we aim to characterize differences in the immunologic response to surgery between inhalational, total intravenous and epidural anesthesia. This will be done by analyzing blood samples obtained in the perioperative period in patients undergoing different modes of anesthesia. We will furthermore describe the quality of recovery for patients anesthetized with the different methods

Objectives

We hypothesize that the immunologic response to surgery and metastasis progression are influenced by the anesthetic technique.

Methods

The study is initiated by Center for Surgical Science, Department of Surgery, Zealand University Hospital. It will be included in the Ph.D. studies of [name] at University of Copenhagen.

Design and approvals

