The first contact with a potential participant will be either during a stable phase of the primary admission, during an out-patient visit or during an introduction meeting prior to surgery. Patients will receive both oral and written information about the study. Patients will be contacted and a meeting where the inclusion will take place will be planned. An appropriately trained investigator will give information about the study including potential risks, harms and inconveniences. Before this meeting, patients will be informed that:

1. The patients have 24 hours or more to consider their informed consent.
2. An observer at the meeting can accompany the patient.

The meeting will take place in a quiet and undisturbed room. Amended to the patient information will be a document from the Central Ethical Committee with the title of "Your rights as a test subject in a biomedical research", which the patient will be recommended to read before inclusion.

Patients will have blood samples taken at four time-points - before surgery, day 1, day 2, day 3 and at the out-patient visit 10-14 days after surgery, where pathology results are given. The patient timeline is outlined in figure 1.

Participation is voluntary and no financial compensation will be given to participants.

Sample size

Study size

Due to the exploratory nature of this study, it is not possible to perform a valid sample size estimation. However, based on a pilot study of 45 patients undergoing laparoscopic hemicolectomy we found that the neutrophil to lymphocyte ratio increased 5.33 neutrophils/lymphocyte from preoperatively to postoperative day 1 (SD 3.33). With a power of 0.8 and an alpha value of 0.05 we will be able to detect a 50% smaller increase in neutrophil to lymphocyte ratio with 25 participants. As this power calculation is associated with much uncertainty we will include 30 evaluable patients (patients completing the study without meeting withdrawal criteria) to avoid a type 2 error.

We estimate that 10-20% of included patients will meet withdrawal criteria before completing the study. Therefore we expect that we need to include 36 patients to complete the study.

They will be compared to the patients included in the IMOX-study at Zealand University Hospital.

Recruitment timeline

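### Does a sample size built on one two-group difference leave the three-technique comparison underpowered?

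*Combined protocol and SAP*

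**What the plan says.** The Study size section uses one pilot of 45 patients, one mean rise from before surgery to day 1 (5.33), one SD (3.33), power 0.8 and alpha 0.05. It concludes that "we will be able to detect a 50% smaller increase in neutrophil to lymphocyte ratio with 25 participants", raises this to 30 evaluable patients, and adds: "They will be compared to the patients included in the IMOX-study at Zealand University Hospital". It gives neither the pilot patients' anesthetic technique nor the contrast to which the 50% applies. The same section says that a valid sample size estimate is not possible and that the calculation is very uncertain.

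Other sections describe three groups. The background says "we aim to characterize differences in the immunologic response to surgery between inhalational, total intravenous and epidural anesthesia". The control-group section says of the 60-patient IMOX cohort: "The population will be stratified according to anesthetic technique", meaning TIVA or sevoflurane. The Data analysis section begins "Data from the Hvidovre population and the Zealand University Hospital population will be combined to evaluate the effects of inhalational anesthesia" and goes on to TIVA and to TIVA with epidural. It names no primary contrast and does not say whether the groups are compared by one overall test or in pairs.

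On direction, the background offers two cautious statements: "volatile inhalational anesthesia is thought to modulate the immune system in a pro-cancerous way, while propofol may have opposite effects", and "Regional anesthesia and amide local anesthetics are suspected to calm the immunologic storm of prostaglandins, catecholamines and cytokines".

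**The concern.** Read together, the background statements suggest an order: the largest response under sevoflurane, a smaller one under TIVA, and the smallest under TIVA with epidural. In that order the gaps add up. A difference of 2.665 at each of two steps would need 2 × 2.665 = 5.33 between the extremes, which equals the entire average rise in the pilot. One power figure therefore cannot hold for all three pairs unless the effects are very large.

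If the 50% describes the distance between the extremes, the comparison of TIVA with epidural against TIVA alone has to detect only part of it. A non-significant result there could be taken as evidence of no epidural effect, under a section that presents the 30 patients as protection against a type 2 error.

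**Working it through.** **Inputs.** From Study size: mean rise 5.33, SD 3.33, a 50% smaller rise, power 0.8, alpha 0.05, 30 evaluable patients. From the statistical analysis plan: two-sided tests. From the control-group section: 60 IMOX patients at most, since those given other techniques are excluded. Assumptions: SD 3.33 in every group, and a range of IMOX splits, because the documents give none.

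**1. Reproduce the 25.** Difference = 0.5 × 5.33 = 2.665; standardised, 2.665 / 3.33 = 0.80.
n per group = 2 × [3.33 × (1.960 + 0.842) / 2.665]² = 24.5, so 25.
The t-test has power 0.79 at 25 v 25 and 0.81 at 26 v 26. The 25 is therefore a number per group in a two-group comparison.

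**2. Power for 2.665 with 30 epidural patients.** SE = 3.33 × √(1/30 + 1/m); noncentrality = 2.665 / SE; power from the noncentral t.

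| Comparator size m | SE | Noncentrality | Power |
|---|---|---|---|
| 15 | 1.053 | 2.53 | 0.70 |
| 23 | 0.923 | 2.89 | 0.81 |
| 30 | 0.860 | 3.10 | 0.86 |
| 37 | 0.818 | 3.26 | 0.89 |
| 60 (all IMOX) | 0.745 | 3.58 | 0.94 |

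**3. The unfavourable reading.** Take 2.665 as the sevoflurane-to-epidural gap, place TIVA between the two, and use 30/30/30.

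| Share of gap due to epidural | Epidural v TIVA: difference | Power | TIVA v sevoflurane: difference | Power |
|---|---|---|---|---|
| 75% | 2.00 | 0.63 | 0.67 | 0.12 |
| 50% | 1.33 | 0.33 | 1.33 | 0.33 |

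Over every TIVA position and every split of 60 IMOX patients, the weaker of these two comparisons peaks at 0.34 (t-test; 36 TIVA and 24 sevoflurane, epidural step 48% of the gap).

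**4. Overall test in the same scenario.** With TIVA midway and 30/30/30, the noncentrality is 30 × (1.3325² + 0² + 1.3325²) / 3.33² = 9.61. The three-group F test (2 and 87 degrees of freedom) then has power 0.78. Midway is the least favourable TIVA position for this test at equal group sizes; at 75/25 it has 0.82.

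**The case for a change.** The strongest case for a change is that the section still uses the calculation to set 30 patients, and that calling the study exploratory excuses uncertainty in the pilot figures without saying which comparison is meant. The readings do give different power for epidural against TIVA: 0.86 if 2.665 is that difference, 0.63 or 0.33 if it is only part of a larger gap. Clarifying this would take a sentence and a count from IMOX.

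The missing label and the arithmetic both stand. Three things limit what follows from them.

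- The low figures need a premise that the documents do not contain. Nothing identifies the 50% with the sevoflurane-to-epidural gap. The background wording is tentative and concerns immune effects related to cancer, not the rise in this ratio. The stated hypothesis is only that technique influences the response.
- The 0.34 is a ceiling for whichever TIVA comparison is weaker, not a figure for the epidural. At a 75/25 split the weak one is TIVA against sevoflurane (0.12). Both of those groups come from IMOX, so recruitment at Hvidovre cannot affect it. Dividing a difference that is only just powered into two steps will always leave a weak step.
- Epidural against TIVA is not a clean test of the epidural, whatever its power. It also compares two hospitals, and the Intervention section states the dexamethasone exception for Hvidovre only.

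**Conclusion.** No change follows. For the comparison that the Study size section itself names, Hvidovre against IMOX, the design gives 0.94 power for 2.665 with all 60 controls. Against a single IMOX stratum it gives at least 0.81 with 23 or more patients. Neither the 25 nor the stated 0.8 is shown to be wrong, apart from the usual difference between the normal approximation and the t-test (25 or 26 per group).

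What remains is missing detail: the words per group, the contrast and the pilot technique. Supplying them would recruit nobody and would leave the group comparisons as they are. An analyst would in any case quote the actual group sizes. Reporting each difference with a 95% confidence interval, with a half-width of about 1.72 at 30 v 30 (2.00 × 0.860), would show that a non-significant result does not exclude a smaller effect.

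The conclusion assumes a common SD of 3.33 and an IMOX stratum of at least 23. The documents do not give the split; with 15 in the stratum, power for 2.665 would be 0.70. IMOX is a cohort of set size, so naming the contrast would not change that number either.

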This study, initiated by Center for Surgical Science, Zealand University Hospital, will be a prospective cohort study. Approval from Danish Data Protection Agency and the Regional Committee for Health Research and Ethics is required. The study will require informed consent from participants.

Permission to transfer data from the IMOX study will be obtained from the Danish Data Protection Agency. The trial protocol will be submitted to clinicaltrials.org before initiation of the trial. Manuscripts will be prepared according to the STROBE statement²⁵.

Study setting

The study will take place at Hvidovre Hospital. This is a Danish university hospital. It supports 500,000 people and is one of four main emergency hospitals in Copenhagen Denmark. About 300 laparoscopic colon resections are performed at this facility every year.

Intervention

Participants will undergo laparoscopic colon resection for cancer. They will be anaesthetized according to the standard operating procedure at Hvidovre Hospital (see appendix 1) with the exception that no dexamethasone is administered as it could modulate the immune response. This includes anesthesia induction and maintenance with intravenous propofol and remifentanyl. Patients will receive 4 mg ondansetron at the end of anesthesia.

A thoracic epidural catheter will be installed preoperatively and kept for up to three days. After an initial bolus with bupivacaine, continuous infusion of bupivacaine and sufentanyl will be used to maintain the epidural analgesic effect. Postoperatively the epidural will be paused or discontinued if it is displaced or if side effects occur. It will only be re-installed if there is still need of neuraxial analgesia.

Patients will follow a standard Enhanced Recovery After Surgery (ERAS) protocol used at the facility.

Blood samples will be obtained before surgery and at four time points postoperatively and patient files will be assessed for adverse events within 30 days from surgery.

Withdrawal criteria:

Patients can be withdrawn from the study for any of the following reasons:

- Failure to adhere to the anesthesia intervention described above- including failure to install effective continuous epidural anesthesia.
- Adverse events after surgery
 - Any complication over grade 2 in Clavien-Dindo²⁶ classification
 - Blood transfusion
 - Deep vein thrombosis or pulmonary embolism
 - Anastomotic leak
 - Acute renal failure

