 - Infection (wound infection or systemic infection) during the observation period.
- After consultation patients can be withdrawn due to withdrawal of informed consent to participate in the study at the patients' own request at any time for any reason.

Population

Study group: The "Hvidovre population":

We will include patients undergoing laparoscopic hemicolectomy for cancer scheduled for anesthesia with total intravenous anesthesia combined with epidural anesthesia on Hvidovre Hospital according to the intervention described above.

Eligibility criteria:

Inclusion criteria:

1. Patients over 18 years
2. Patients diagnosed with colorectal cancer (UICC stadium I-III) and scheduled for laparoscopic hemicolectomy.
3. ASA class I-III (Classification of the American Society of Anesthesiology)

4. Patients scheduled for anesthesia with propofol, remifentanil and epidural anesthesia.
5. Signed informed consent

Exclusion criteria:

1. Known immune-defects
2. Patients undergoing neoadjuvant chemo or radiotherapy
3. History of previous cancer
4. Patients in immunomodulatory treatment within last 6 months
5. Daily oral or intravenous steroid-use
6. Patients that have undergone major surgery within one month before planned colon resection.

Control group: The “Zealand University Hospital population”

The immunological and oxidative stress in relation to abdominal surgery (IMOX) study is ongoing at Zealand University Hospital, Roskilde. It is a prospective explorative study cohort that consists of 60 patients undergoing laparoscopic colorectal cancer surgery. The aim of the study is to characterize the immunological and oxidative stress response to surgery. Outcomes similar to the primary and secondary outcomes of the ANIMOX-study are included in the IMOX-study. Patients are already included in the IMOX-study and blood samples are collected and kept in a bio bank.

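### The evaluable Hvidovre set drops patients for complications, most of which can arise after the day-1 primary endpoint is measured, and no matching rule is stated for the IMOX controls

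*Combined protocol and SAP*

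**What the plan says.** The Study size section sets the target for the Hvidovre arm as "30 evaluable patients (patients completing the study without meeting withdrawal criteria"). It expects 10–20% of included patients to meet those criteria and so plans to include 36. The Recruitment timeline repeats the same definition of the 30.

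The Withdrawal criteria section opens with "Patients can be withdrawn from the study for any of the following reasons". The reasons are of three kinds:
- failure of technique: "Failure to adhere to the anesthesia intervention described above- including failure to install effective continuous epidural anesthesia";
- post-operative events: "Any complication over grade 2 in Clavien-Dindo", transfusion, deep vein thrombosis or pulmonary embolism, anastomotic leak, acute renal failure, and "Infection (wound infection or systemic infection) during the observation period";
- withdrawn consent.

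The observation period is not defined. Blood sampling runs to day 10–14, and adverse events are collected for 30 days.

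On the endpoint: "The primary outcome will be changes in neutrophil to lymphocyte ratio from day 0 to day 1". The same section adds: "Neutrophil to lymphocyte ratio has been linked to poor outcome after colorectal cancer surgery".

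For the controls, the Control group section gives one exclusion: "Patients anaesthetized with other techniques including epidural or other regional blocks will be excluded from the analysis". The Data analysis section pools the two cohorts by technique. It does not say which patients are analysed, or whether the day-1 value of a withdrawn patient is kept.

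**The concern.** An anastomotic leak or wound infection on, say, day 6 cannot make a day-1 NLR missing or invalid, yet under the Study size definition that patient is no longer evaluable. If the evaluable patients are the ones analysed, the epidural arm is conditioned on an uncomplicated course after exposure. The control arms, as far as the documents state, are not.

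If patients who go on to complications already have a larger NLR rise on day 1, removing them lowers the Hvidovre mean and favours epidural. The protocol's own remark on NLR and poor outcome makes that direction plausible. It does not quantify any link between the day-1 change and later complications.

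There is a second risk. The withdrawal wording is permissive, results are available in the patient record as soon as they are analysed, and nothing says the decision is made without sight of them. A removal decision could therefore follow knowledge of the day-1 value.

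**Working it through.** **Inputs from the protocol (Study size, Statistical analysis plan).** Mean NLR rise 5.33; SD 3.33; target a 50% smaller rise; power 0.80; alpha 0.05, two-sided; 30 evaluable from 36 included; 10–20% meeting withdrawal criteria for any reason.

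**Reproducing the plan's figures.**
- Target difference: 0.5 × 5.33 = 2.665.
- n per group = 2 × (1.960 + 0.842)² × (3.33 / 2.665)² = 24.5, so 25. This matches the stated 25, read as per group.
- Inclusion: 30 / (1 − 1/6) = 36. The stated range of losses gives 34 (10%) to 38 (20%). The 36 is consistent.

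The sample-size arithmetic is not in question.

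**Assumptions.** The documents do not give:
- *p*, the share of Hvidovre patients removed for complications. Taken as 5–20%. The top value treats every withdrawal at the plan's upper estimate as a complication.
- *e*, the amount by which the removed patients' day-1 rise exceeds that of the kept patients, in SDs. Taken as 0–1.0.
- The number of IMOX controls per technique. Taken as 30, then 20 and 40.

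**Formula.** Shift in the Hvidovre mean = p × e × 3.33. With no true difference, the test statistic is noncentral t with 58 degrees of freedom and noncentrality shift / SE, where SE = 3.33 × √(1/30 + 1/30) = 0.860.

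| p | e | Shift (NLR units) | % of 2.665 | Type I error, 30 v 30 |
|---|---|---|---|---|
| any | 0 | 0 | 0 | 5.0% |
| 0.05 | 0.5 | 0.083 | 3.1 | 5.1% |
| 0.05 | 1.0 | 0.167 | 6.2 | 5.4% |
| 0.10 | 0.5 | 0.167 | 6.2 | 5.4% |
| 0.10 | 1.0 | 0.333 | 12.5 | 6.7% |
| 1/6 | 1.0 | 0.555 | 20.8 | 9.7% |
| 0.20 | 0.5 | 0.333 | 12.5 | 6.7% |
| 0.20 | 1.0 | 0.666 | 25.0 | 11.9% |

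For the last row, 20 controls give 10.4% and 40 controls give 12.9%.

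**Check by simulation.** Filtering only the Hvidovre arm at p = 0.20, e = 1.0 gave 11.3% and 12.2% in two separate simulations, in line with the formula. Applying the same filter to both cohorts returned 4.9%. The inflation therefore comes from the one-sided filter, not from the filter as such.

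**Power if the patients are kept.** Two-sample t test for 2.665 units against 30 controls (assumed): 0.86 with 30 Hvidovre patients, 0.89 with all 36.

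**The case against.** The strongest reply is that exclusion from the analysis is inferred. The evaluable definition appears only in the sample-size and recruitment text, where it sets how many to enrol. The Data analysis section speaks of the Hvidovre population, which the Population section defines by eligibility. The sentence about comparison with IMOX follows the figure of 36 and could mean all included patients. This is a fair reading, but the less likely one: inflating from 30 to 36 to make up for patients who meet the criteria has little purpose if they are analysed anyway. Under either reading the analysis set must be stated.

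Second, IMOX may have an equivalent rule in its own protocol, which is not among the documents. That stands: if it does, this bias disappears.

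Third, the excess rise is assumed, and the top of the range needs every withdrawal to be a complication, although failed epidural and withdrawn consent are also counted. If only half of withdrawals are complications (5–10%), an excess of 0.5–1.0 SD gives 0.08–0.33 units and a type I error of 5.1–6.7%. At an excess of 0.25 SD the error is at most 5.4%, even with 20% removed. Much of the grid is close to nominal.

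Fourth, the automatic rule in Study size and the discretionary one in Withdrawal criteria are alternatives, so their risks should not be added together. That is right.

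Finally, some events, such as a transfusion, may fall before the day-1 sample, and removing complicated patients has a rationale for the later samples. Neither point justifies the rule for a primary endpoint that ends on day 1.

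**Conclusion.** The concern holds and should be fixed. Read as written, the plan selects the epidural arm on events after exposure, states no counterpart for the controls, and leaves the analysis set undefined. The direction, favouring epidural, is plausible but not established by the documents.

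The size ranges from nothing, if complicated patients have no larger day-1 rise or IMOX applied the same rule, to about a quarter of the target difference with a type I error near 12% at 30 v 30. That upper figure rests on 20% removed for complications and a 1 SD excess. Smaller values are more likely if complications make up only part of the withdrawals. The study calls itself exploratory, but it names a primary outcome, a power calculation and a 5% significance level, so an avoidable asymmetry in a non-randomised comparison of two hospitals deserves removal.

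**What to change.** Define the primary analysis set in the statistical analysis plan:
- Include every consenting Hvidovre patient who received the study anaesthetic technique and has a pre-operative and a day-1 sample, whatever complication, transfusion or infection occurs. Report those events as outcomes, not as grounds for leaving the set.
- Treat failed epidural as a separate technique-based rule, parallel to the technique filter on IMOX. Judge it only on information available up to the day-1 sample and without sight of the NLR result.
- State which event-based exclusions, if any, IMOX applied.
- Report the complication-free subset as a sensitivity analysis, with identical event rules in both cohorts.

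The cost is wording in the withdrawal, sample-size and analysis sections, plus event data from IMOX for the sensitivity analysis. The protocol describes retrieving IMOX data on the main outcomes, so the event data may need to be covered by the data-transfer permission, and the change may need committee approval. No extra patients or procedures are required, and power rises slightly. The downside is that some NLR values, mainly at later time points, will reflect complication-related inflammation. The sensitivity analysis addresses this.
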